4. PARTICIPANT ENTRY

4.1 PRE-REGISTRATION EVALUATIONS

Children will be recruited from the outpatient clinics at the Royal Brompton Hospital

Written information regarding the study (the patient information sheet) and contact details of the study team will be given to parents

Written, informed consent from the parent / guardian and consent (if appropriate) or assent from the child will be obtained by a member of the study team prior to undertaking any study procedures. "Informed consent" requires individual discussion with the child and their parent / guardian about the study and the nature of the procedures to be conducted in a language that is easy to comprehend. The child and their parent /guardian will be given adequate time to decide whether or not they wish to participate. The child and their parent / guardian should understand that his / her refusal to participate in the study will not affect their subsequent medical care and if they do consent they may withdraw at any point without affecting their care.

The participant consent form must be signed by a member of the study team to confirm that informed consent was obtained. The original of the signed declaration of consent will be stored in the case notes. A copy will be given to the parent / guardian

Information sharing

Consent will be sought to inform the child's GP and usual hospital consultant of their enrolment in the study. If clinically important information is found as a result of the study this will be discussed with the participant and their parent / guardian and their consent sought to share this information with their GP and / or other relevant medical professionals.

Follow up of participants after study completion

At the end of the study (as a result of study completion or withdrawal) participants will continue to receive their usual clinical care.

4.2 INCLUSION CRITERIA

A child will be included in the study if the following criteria applies:

- Informed consent obtained from parents/guardian/adolescents and/or assent from the child.
- Children aged between 6-16 years with a diagnosis of asthma attending the Royal Brompton and Harefield Difficult asthma clinic.
- Children on inhaled corticosteroids
- Parents/ young person has a mobile phone which can download apps
- Paediatric respiratory nurses working in the difficult asthma team at Royal Brompton Hospital.

4.3 EXCLUSION CRITERIA

A child will not be eligible for the study if the following applies:

- Unable to provide consent
- As a result of medical interview, physical examination or screening investigation the physician responsible considers the child unfit for the study.
- Those who, in the opinion of the investigator, have a risk of non-compliance with study procedures
- Children under the age of 6 years.
- Children not on inhaled corticosteroid
- It is not anticipated that any children will be pregnant, however, if they are they will not be included in the study

4.4 WITHDRAWAL CRITERIA

Children/parents/carers may withdraw any time without affecting their treatment or care.

If adherence data has been collected for > 8 weeks of treatment then permission will be requested to use this data from parents/carers. If data has not been collected for > 8 weeks then this will not be used.

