APPENDIX 1. SUMMARY OF INVESTIGATIONS, TREATMENT AND ASSESSMENTS		
	24	

GLOSSARY OF ABBREVIATIONS

KEYWORDS

Electronic monitoring device (EMD)
Novel electronic monitoring device (NEMD)
Compliance
Adherence
Children
Asthma

STUDY SUMMARY

TITLE	A feasibility study to assess novel electronic monitoring devices for monitoring adherence in children with asthma
DESIGN	A mixed method (quantitative and qualitative) open label, block randomised feasibility study
AIMS	
 1. To assess the feasibility of 4 novel electronic monitoring devices in children aged 6-16 years with asthma, in terms of usability and acceptability by patients/ guardians and healthcare professionals (qualitative study) 2. To evaluate the accuracy of these devices and assess whether they impact on asthma control (quantitative study)
OUTCOME MEASURES	
Primary outcome: Acceptability and usability of devices to participants and healthcare professional at Royal Brompton and Harefield NHS foundation Trust (RBHT)
 
Secondary outcomes:
 
 1. Accuracy of the adherence data collected from the devices. 2. Effect on asthma control as measured by asthma control test (ACT) or childhood asthma control test (cACT) score; exhaled nitric oxide (FENO), spirometry (FEV1) and bronchodilator reversibility (BDR).
POPULATION	Children aged 6-16 years with asthma on inhaled corticosteroid therapy.
ELIGIBILITY	Children aged 6-16 years with a diagnosis of asthma on inhaled corticosteroids who are being treated or followed up by the paediatric respiratory difficult asthma clinic at Royal Brompton hospital.
DURATION	Up to 16 weeks

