2. STUDY OBJECTIVES

Research question: Which novel electronic monitoring device (NEMD) (measuring both inhalation & activation) is the most feasible to use as a tool for monitoring adherence in children aged 6-16 years with asthma in terms of accuracy, usability and acceptability?

Aim: To conduct a feasibility study looking at four new electronic monitoring devices to monitor adherence in children with asthma aged 6-16 years prescribed inhaled corticosteroids.

Our primary objective is to assess which novel electronic monitoring device is the most feasible to use as a tool for monitoring adherence in children with asthma, in terms of its perceived accuracy, usability and acceptability by patients/guardians and healthcare professionals by using a face to face focus group discussion meeting or one to one interviews.

For the purposes of this study feasibility is the overarching term used to assess if the devices are capable of being used in clinical practice to monitor adherence.

Accuracy of the device will be assessed by capturing usable data from the devices. Usability of the device will be assessed from the focus group or one to one interviews encompassing ease of use, time taken, problems encountered, easy to learn to use the device.

Acceptability will also be assessed from the focus group discussions or one to one interviews in terms of aesthetically pleasing, liked the device, fits in with day to day living.

Our secondary objective is to evaluate the effect on asthma control as measured by asthma control test (ACT) or childhood asthma control test (CACT) score; exhaled nitric oxide (FENO), spirometry (FEV1) and bronchodilator reversibility (BDR)

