All children will be issued with a novel electronic monitoring device which will be attached to the child's usual inhaler or require an app on their mobile phone as described above. Parents and children will be provided information and advice on the use of the novel electronic monitoring device and asked to conduct up to 16 weeks of home monitoring using their allocated NEMD on their first visit.

Information on how to contact the team in case of any problems will be related to the participant in both oral and written form.

The data will be stored electronically and downloaded at the next clinic visit.

Contact by telephone will be made at day 7-14 to ensure that the device is working and to answer any other queries then at week 6-7 to determine if the device is being used appropriately and to answer any related questions.

Week 1 - for the rDOT arm, adherence data will be downloaded to check for consistencies in inhaler technique. If inhaler technique is inaccurate, the participants will be called by the respiratory nurse specialists to advise on correct technique. This will be documented as part of the data collection.

Week 4 – All devices, adherence data will be downloaded and checked to ensure that the devices are working correctly.

Visit 2: up to 16 weeks of adherence data collection

Routine clinical care assessments will be carried out at the end of the study period as below, including asthma control test (ACT) or the childhood asthma control test (cACT), exhaled nitric oxide and spirometry (FEV1 and BDR) .

Adherence data will be downloaded at the end of the study period and stored electronically.

Visit 3: Focus group or one to one interviews

The participants and their carers will be invited to a face to face focus group interview, or a one to one interview, depending on their availability at the end of the study period. The focus group and one to one interviews will utilise a semi structured questionnaire, to provide qualitative feedback on the acceptability and usability of the devices.

A separate focus group meeting will also be conducted with the paediatric respiratory nurses who are part of the MDT to assess their views on the devices used as they routinely provided all asthma devices and are also involved in downloading data from other devices that we would use as part of routine care (smart-inhaler). They will also be consented to take part in the study

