Where possible a second researcher from University College London (UCL), [name] will sit in the focus groups discussion and interviews to ensure there is no bias.

The conversations from the focus group and one to one interviews will be transcribed and coded into themes. We will utilise an external company for transcribing the conversations called 1st Class. <https://www.1stclass.uk.com/>

Analysis

Qualitative:

The focus group and one to one interviews will be audio recorded, transcribed and put into themes to conduct an inductive thematic analysis. 25% of the transcripts (8) will be double coded by an independent researcher from UCL, [name], experienced in qualitative research to ensure that the correct themes have been used and to ensure that there is no bias.

The focus group and one to one interviews will be used to assess the usability and acceptability of the devices

Quantitative:

[figure not shown]
The amount of usable data from each device will be quantified and compared.

This will provide data on the perceived accuracy of the device.

The quantitative and qualitative results will be amalgamated and an evidence report prepared to assess the feasibility of each device.

An expert panel will be convened to select the most appropriate device to take forward to a larger randomised controlled trial to assess the impact of the device on adherence in children with asthma.

REFERENCE DIAGRAM

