The focus group interviews will be used to assess the usability and acceptability of the devices

➤ Quantitative data

The amount of usable data from each device will be quantified and compared.

This will provide data on the perceived accuracy of the device.

Additionally, data on asthma control and quality of life will be assessed.

These will be analysed quantitatively statically using the Statistical Package for the Social Services (SPSS). Data will be tested for normality using visual inspection, histograms and Kolmogorov-Smirnov testing. Parametric tests will be used if the data is normally distributed. If the data is not normally distributed or there are only small numbers non parametric tests will be used or the data will be logarithmically transformed. The significance levels for all tests will be set at <0.5.

Comparative analysis of variance between 2 groups for continuous data will be performed using the student's t test for normally distributed data and the Mann Whitney U tests for non normally distributed data and for more than 2 groups the ANOVA or Kruskal Wallis respectively. A comparison of the proportions between groups will be performed using the Pearson Chi 2 tests.

The quantitative and qualitative results will be amalgamated and an evidence report prepared to assess the feasibility of each device.

An expert panel will be convened to select the most appropriate device to take forward to a larger randomised controlled trial to assess the impact of the device on adherence in children with asthma.

Data and all appropriate documentation will be stored for a minimum of 10 years after the completion of the study, including the follow-up period.

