8.2 CONSENT

Consent to enter the study will be sought from each participant only after a full explanation has been given, an information leaflet offered and time allowed for consideration. Signed participant consent will be obtained. The right of the participant to refuse to participate without

giving reasons must be respected. After the participant has entered the study the clinician will remain free to give alternative treatment to that specified in the protocol at any stage if he/she feels it is in the participant's best interest, but the reasons for doing so will be recorded. In these cases the participants will remain within the study for the purposes of follow-up and data analysis. All participants are free to withdraw at any time from the protocol treatment without giving reasons and without prejudicing further treatment.

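### Section 4.4 discards device data from children who withdraw with 8 weeks or less collected, which can bias the usable-data comparison between devices

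*Combined protocol and SAP*

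**What the plan says.** Section 4.4 allows withdrawal at any time. Where more than 8 weeks of adherence data exist, parents or carers are asked whether the data may be used. Below that, the rule is absolute: "If data has not been collected for > 8 weeks then this will not be used".

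The Study Summary lists as its first secondary outcome "Accuracy of the adherence data collected from the devices". Section 2 says how this is judged: "Accuracy of the device will be assessed by capturing usable data from the devices". Sections 3 and 7 both set the comparison: "The amount of usable data from each device will be quantified and compared". The result is merged with the interview findings into a report on each device, after which "An expert panel will be convened to select the most appropriate device to take forward to a larger randomised controlled trial".

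Section 3 plans 30 children. Smartinhaler Plus and rDOT have 10 each; Flo-Tone/Rafi-tone and INCA have 5 each. Home monitoring lasts up to 16 weeks. At week 4, for all devices, "adherence data will be downloaded and checked to ensure that the devices are working correctly", so data can already be in hand for a child who leaves early.

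**The concern.** A child can leave because the device failed, was a burden or was disliked. Those are the events a feasibility study of devices needs to see. The rule removes such a child's device data from the quantitative evidence, even where the family would have agreed to its use.

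The effect depends on how the amount of usable data is expressed. If results are given per contributing child, early leavers drop out of sight together with any poor capture they had. If they are given as totals or per allocated child, data that the device did capture are deleted. Either way, a device that loses more children early is treated differently from one that keeps them, and the panel would be comparing devices on unequal terms.

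**Working it through.** **Plan's own figures.** The only sample-size figure, 29 participants for themes of 10% prevalence seen at least twice with 80% probability, reproduces: the exact binomial probability is 0.8011 at n=29 and 0.7848 at n=28. It concerns interview themes and does not bear on this rule. The readable text gives no withdrawal rate, capture rate or denominator for usable data, so what follows is illustration.

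**Inputs.** From the protocol: T = 16 weeks (the maximum), n = 10 or 5 per device, cut-off 8 weeks. Assumed: capture in stayers c = 0.90, one withdrawal (k = 1) at week w = 6, capture in the leaver l = 0.90, 0.50 or 0.20.

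**A. Usable time over planned time, l = 0.90.**
- All data kept: [(n−k)·16·c + k·w·l] / (16n)
- Rule deletes the child's data only: (n−k)·16·c / (16n)
- Rule removes the child from numerator and denominator: c

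| | All data kept | Data deleted, child counted | Child removed |
|---|---|---|---|
| n=10 | (129.6 + 5.4)/160 = 84.4% | 129.6/160 = 81.0% | 129.6/144 = 90% |
| n=5 | (57.6 + 5.4)/80 = 78.8% | 57.6/80 = 72.0% | 57.6/64 = 90% |

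The rule moves the figure down in one reading and up in the other. Section 4.4 does not say which applies.

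**B. Usable time over time in the study.** All data kept: [(n−k)·16·c + k·w·l] / [(n−k)·16 + k·w]. Rule applied: c = 90%.

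| Leaver's capture | n=10, all data kept | n=5, all data kept | Rule |
|---|---|---|---|
| 90% | 135.0/150 = 90% | 63.0/70 = 90% | 90% |
| 50% | 132.6/150 = 88.4% | 60.6/70 = 86.6% | 90% |
| 20% | 130.8/150 = 87.2% | 58.8/70 = 84.0% | 90% |

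**Timing.** Under A with only the data deleted, the loss is w·l/(16n). With l = 0.90:
- week 4: 3.6/160 = 2.3 points (n=10), 3.6/80 = 4.5 points (n=5);
- week 6: 3.4 and 6.8 points;
- week 8: 4.5 and 9.0 points.

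**Other assumptions.** Take 80% capture in stayers and one leaver at week 4 with 40%. Over planned time, keeping all data gives (115.2 + 1.6)/160 = 73% (n=10) or (51.2 + 1.6)/80 = 66% (n=5), against 80% with the child removed. Over time in the study it gives 116.8/148 = 78.9% or 52.8/68 = 77.6%, again against 80%. The same rule therefore hides 7 and 14 points on one denominator and about 1 and 2 on the other.

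**The case against.** The rule may be meant to respect a family's decision to leave, and the consent pages are not in the copy reviewed. The study is largely qualitative, the measure is secondary, and the panel reads a combined report and does not rank devices by one number. Section 4.3 excludes children judged likely not to comply, which may reduce early withdrawal. Section 4.4 restricts adherence data, not records of device problems. The calls at day 7–14 and week 6–7, and the separate focus group with the nurses who issue and download devices, may carry some leavers' problems to the panel. All of this stands. It limits the consequence but does not restore the discarded data to the comparison. Section 8.2 does not cancel the rule either: its provision for staying in the analysis covers children whose clinician gives alternative treatment.

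Three stronger readings are tempting, and the documents do not support them.
- **Withdrawn families are left out of the interviews.** Section 3 says "The participants and their carers will be invited to a face to face focus group interview, or a one to one interview" at the end of the study period, and section 4.1 counts withdrawal as one way the study ends. Whether leavers are invited is ambiguous.
- **No count of withdrawals by device is planned.** The readable text states none, but a figure beside the quantitative analysis and the reference diagram in section 3 are not shown.
- **The rule flatters poorly tolerated devices by a known amount.** The working shows that direction and size both change with the assumptions.

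**Conclusion.** The point holds as a minor one. As written, the plan drops outcome data according to an event that follows allocation and may be caused by the device, so the usable-data comparison can be biased. In the week-6 illustration, one early withdrawal shifts a device's figure by anything from nothing to 5.6 points with 10 children (90 − 84.4) or 11.25 points with 5 (90 − 78.75), in either direction. These are not bounds. They rest on assumed capture and timing, on a full 16 weeks although the protocol says up to 16, and on all six weeks being recoverable.

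If withdrawal is unrelated to the device and to capture, a rate per day in the study is not biased and the loss is mainly of precision. A reader might infer that the rule could lead the panel to the wrong device. The documents do not show that, because no withdrawal rate is given and the choice draws on the qualitative findings too.

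**What to change.** 1. Replace the 8-week discard with permission, sought at consent, to use all device data collected up to withdrawal, whatever the duration. Keep the restriction to more than 8 weeks only as a sensitivity analysis.
2. For each device and all allocated children, report usable days divided by days in the study with the device. Beside it, give the number and timing of withdrawals, with reasons where the family offers one. Reasons must stay voluntary, since section 8.2 says "All participants are free to withdraw at any time from the protocol treatment without giving reasons".
3. State whether withdrawn families are still invited to interview.

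The cost is revised protocol and consent wording, plus a withdrawal date and an optional reason field on the CRF. Some families may refuse the wider permission. Data recorded after the last download may be lost if a device is not returned. Reasons will be incomplete, and capture figures may look less favourable.

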5. ASSESSMENT AND FOLLOW-UP

No study assessments will take place until written informed consent and age appropriate assent is obtained.

Routine clinical care data will be collected at the baseline visit and at the end of the study as follows:

Routine clinical care monitoring tests

Routine clinical care test to assess	Test	Visit 1: Study entry	Visit 2: completion of study
Asthma control	ACT/cACT	√	√
Spirometry	FEV ₁ /FVC/BDR	√	√
Inflammation	FeNO	√	√
Asthma related quality of life questionnaire	PAQLQ/PACQLQ	√	√
Prescription uptake		√	√
Drug history		√	
Data downloaded from device: Routine clinical care would be to download from smartinhaler	Data downloaded from new device		√

The main difference between data collection in this study and routine clinical care monitoring is that data will be downloaded from the new devices (NEMD) in comparison to the current smartinhaler device

6. ADVERSE EVENTS

6.1 DEFINITIONS

Adverse Event (AE): any untoward medical occurrence in a patient or clinical study subject.

Serious Adverse Event (SAE): any untoward and unexpected medical occurrence or effect that:

- **Results in death**

- **Is life-threatening** – refers to an event in which the subject was at risk of death at the time of the event; it does not refer to an event which hypothetically might have caused death if it were more severe
- **Requires hospitalisation, or prolongation of existing inpatients' hospitalisation**
- **Results in persistent or significant disability or incapacity**
- **Is a congenital anomaly or birth defect**

Medical judgement will be exercised in deciding whether an AE is serious in other situations. Important AEs that are not immediately life-threatening or do not result in death or hospitalisation but may jeopardise the subject or may require intervention to prevent one of the other outcomes listed in the definition above, should also be considered serious.

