6.2 REPORTING PROCEDURES

All adverse events will be reported. Depending on the nature of the event the reporting procedures below will be followed. Any questions concerning adverse event reporting should be directed to the Chief Investigator in the first instance.

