6.2.1 Non serious AEs

All such events, whether expected or not, will be recorded.

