6.2.2 Serious AEs

An SAE form will be completed and faxed to the Chief Investigator within 24 hours. However, relapse and death due to asthma and hospitalisations for elective treatment of a pre-existing condition do not need reporting as SAEs.

All SAEs should be reported to [name] where in the opinion of the Chief Investigator, the event was:

- ‘related’, ie resulted from the administration of any of the research procedures; and
- ‘unexpected’, ie an event that is not listed in the protocol as an expected occurrence

Reports of related and unexpected SAEs will be submitted within 15 days of the Chief Investigator becoming aware of the event, using the NRES SAE form for non-IMP studies. The Chief Investigator will also notify the Sponsor of all SAEs.

Any SAEs will be reported as required by the Local Research Ethics Committee, Sponsor and/or Research & Development Office.

There are no known SAEs from the use of these devices

It is not anticipated that there will be any SAE's with the use of the devices, however, should anything occur as a result of the device then the child will be followed up daily in the first instance then weekly for the next four weeks.

A period of four weeks of follow up care will occur after the last treatment for any adverse events to be recorded and reported.

Contact details for reporting SAEs

Fax: xxx, attention xxx

Please send SAE forms to: [name], Pharmacy Department, Royal Brompton Hospital.

[contact] [name] (Mon to Fri 09.00 – 17.00)

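### The SAE definition in section 6.1 includes expectedness, which contradicts section 6.2.2 and leaves expected serious events without a clear reporting route

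*Combined protocol and SAP*

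**What the plan says.** Section 6.1 gives two definitions. An adverse event is "any untoward medical occurrence in a patient or clinical study subject", with no condition on expectedness. A serious adverse event is "any untoward and unexpected medical occurrence or effect that" leads to one of five listed outcomes, among them death and hospitalisation. A closing paragraph adds a further route to seriousness: "Medical judgement will be exercised in deciding whether an AE is serious in other situations".

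Section 6.2 opens with a general rule, "All adverse events will be reported", and says that the procedure depends on the nature of the event. Two procedures follow.

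- Section 6.2.1, headed for non-serious events: "All such events, whether expected or not, will be recorded".
- Section 6.2.2, for serious events: "An SAE form will be completed and faxed to the Chief Investigator within 24 hours". It exempts asthma relapse, asthma death and elective admissions for a pre-existing condition from reporting as SAEs. It then selects for a 15-day report those SAEs that are both related and unexpected, the latter explained as "an event that is not listed in the protocol as an expected occurrence". It also states: "The Chief Investigator will also notify the Sponsor of all SAEs".

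**The concern.** Seriousness describes the outcome of an event. Expectedness describes whether the event was foreseen. Section 6.1 merges the two, while 6.2.2 handles expectedness as a separate question asked about events that are already SAEs. Both cannot be operative as written.

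The 24-hour form and the Sponsor notice apply to SAEs, so both inherit the 6.1 definition. If that definition leaves out expected events, a child's admission or death that staff regard as foreseeable need not go on the form or to the Sponsor. The participants come from a difficult-asthma clinic, where some serious events may well be thought foreseeable. Two members of staff could classify the same admission differently and both be following the protocol. A statement at the end of the study that no SAEs occurred would then be hard to interpret.

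**Working it through.** The plan states no figure on this point and no arithmetic applies. The check sets the clauses side by side.

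**1. Does the expectedness condition in 6.2.2 do any work under the 6.1 definition?** Under 6.1, an SAE is an event that is serious in outcome and unexpected. The 15-day report takes SAEs that are related and unexpected. If the word has the same meaning in both places, every SAE is already unexpected and the second test removes nothing. If it has two meanings, the protocol does not say so, and 6.1 leaves its own undefined. Either way the two sections need to be reconciled.

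**2. Do the other clauses assume that an SAE can be expected?** The exemptions in 6.2.2 for asthma relapse and asthma death cover events that are among the most foreseeable in this population. They would be largely unnecessary if expected events were already outside the definition. The natural inference is that 6.2.2 assumes SAEs include expected events, and that the wording in 6.1 is out of line with it.

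**3. Where does each kind of event go?** Each event below meets a listed outcome in 6.1.

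| Event | SAE under 6.1 as written | 24-hour form and Sponsor notice | 15-day report |
|---|---|---|---|
| Unexpected, not exempt | Yes | Required | If related |
| Expected, not exempt | No | Not required | No |
| Exempt under 6.2.2 | Depends on expectedness | Exempt from SAE reporting in either case | No |
| Expected, not exempt, after the fix | Yes | Required | No |

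Only the second row changes, and it becomes the fourth. The 15-day report is unaffected, because 6.2.2 still applies expectedness there.

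**4. Do the other provisions cover the second row?**

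- The general rule in 6.2 does apply, since the AE definition has no expectedness condition. It refers on to the two procedures, however. The first is headed for non-serious events and requires recording only; the second is for SAEs. An expected admission fits neither cleanly.
- The medical-judgement route has no expectedness condition. It is for situations other than the listed outcomes, and the sentence that follows it concerns events not resulting in death or hospitalisation. It does not clearly bring back an expected death or admission.

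**5. How many events could fall in the second row?** That depends on which meaning of unexpected governs 6.1.

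- *List-based meaning, from 6.2.2.* The protocol contains no list of expected occurrences beyond, arguably, the exempted events, and 6.2.2 says no SAEs are known from the devices. Almost every non-exempt serious event would then count as unexpected, and the second row would be nearly empty.
- *Clinical meaning.* The second row holds any serious event that staff consider foreseeable and that is not already exempt.

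Section 6.1 does not refer to the explanation in 6.2.2, so the documents do not settle the choice.

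**The case against.** The strongest reply is that the protocol supplies its own meaning of unexpected in 6.2.2, by reference to a list, and that on this meaning the extra word in 6.1 excludes almost nothing beyond the exempted events. The point would then be one of loose drafting. The clearest loss of serious events from SAE reporting would be the explicit exemption for asthma relapse and asthma death, which deleting two words does not touch. This argument stands as a limit on practical reach. It does not remove the contradiction, because nothing in 6.1 adopts the list-based meaning and there is no separate list to apply.

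Three stronger readings are tempting, and the documents do not support them.

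- A reader might infer that expected serious events drop out of the safety record altogether. The general rule in 6.2 requires every adverse event to be reported. What is at risk is the route: the form and the Sponsor notice.
- A reader might infer that a safety comparison between devices would be distorted. No per-device safety tally or other safety analysis is planned. The stated outcomes are acceptability, usability, accuracy of the adherence data and asthma control.
- A reader might try to count the events missed. The documents give no rates of serious events, and in this clinic many such events could be asthma relapses that 6.2.2 already exempts.

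**Conclusion.** The point holds as an internal contradiction in an operative safety rule. On its plain wording, 6.1 takes expected serious events out of the SAE category, so they trigger neither the 24-hour form nor the notice to the Sponsor. They remain reportable as adverse events, with no procedure that clearly fits them.

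The size cannot be stated as a number. It ranges from close to nothing, if the 6.2.2 meaning of unexpected governs 6.1, to every foreseeable serious event not already exempt, if expectedness is judged clinically. The conclusion about wording assumes only that 6.1 is read as written. Any conclusion about how many events are affected would need both the intended meaning and event rates, and the documents give neither. No planned efficacy or feasibility analysis depends on the answer; the issue is safety oversight.

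**What to change.** Delete the words *and unexpected* from the SAE definition in section 6.1, so that seriousness rests on the listed outcomes and the medical-judgement paragraph. Keep relatedness and expectedness only in section 6.2.2, as the filter for the 15-day report. Reconcile the exemptions in 6.2.2 with the corrected definition, so that the text makes clear whether an exempted event is an SAE that is not reported as one, and how it is recorded.

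The cost is two words, a check of the exemption paragraph, and a few more SAE forms in a study of 30 children. The 15-day reporting workload does not change.
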